21.3 Observation Period for Adverse Events

The period of observation for AEs and SAEs for each participant will extend from the time of the participant providing written informed consent until completion of the post-treatment follow-up visit scheduled to occur 28-35 days after the last study visit on day 168/week 24. Participants will be instructed to report any adverse event that they experience to the Investigator, whether or not they think the event is due to study treatment.

21.4 Follow-Up of Adverse Events

Every effort will be made to follow AEs until resolution or stabilization. Ongoing, unrelated, nonserious AEs that have not resolved or stabilized and are not clinically significant will be followed until the participant completes the study. Serious adverse events will be followed until the SAE resolves, stabilizes, the participant is lost to follow-up, or death.

22.0 PREGNANCY

A pregnancy occurring during the study is not considered an AE or SAE. In the event of pregnancy, the participant will immediately discontinue the study drug ixazomib and will be discontinued from the study following early completion of the post-treatment follow-up visit scheduled day 196-203 (week 28-29) and in the extension study day 196-203 (week 48).

23.0 REPORTING TO TAKEDA

23.1 Adverse Events

AEs may be spontaneously reported by the patient and/or in response to an open question from study personnel or revealed by observation, physical examination, or other diagnostic procedures. Any clinically relevant deterioration in laboratory assessments or other clinical finding is considered an AE. When possible, signs and symptoms indicating a common underlying pathology should be noted as one comprehensive event. For serious AEs, the investigator must determine both the intensity of the event and the relationship of the event to study drug administration.

AEs which are serious must be reported to Takeda Pharmacovigilance (or designee) from the first dose of study drug through 30 days after administration of the last dose of ixazomib. Any SAE that occurs at any time after completion of ixazomib treatment or after the designated follow-up period that the sponsor-investigator and/or sub-investigator considers to be related to any study drug must be reported to Takeda Pharmacovigilance (or designee). In addition, new primary malignancies that occur during the follow-up periods must be reported, regardless of causality to study regimen, for a minimum of three years after the last dose of the investigational product, starting from the first dose of study drug. All new cases of primary malignancy must be reported to Takeda Pharmacovigilance (or designee).

Planned hospital admissions or surgical procedures for an illness or disease that existed before the patient was enrolled in the trial are not to be considered AEs unless the condition deteriorated in an unexpected manner during the trial (e.g., surgery was performed earlier or later than planned). All SAEs should be monitored until they are resolved or are clearly determined to be due to a patient's stable or chronic condition or intercurrent illness.

Since this is an investigator-initiated study, the principal investigator, [name], also referred to as the sponsor-investigator, is responsible for reporting serious adverse events (SAEs) to any regulatory agency and to the sponsor-investigator's IRB.

Regardless of expectedness or causality, all SAEs (including serious pretreatment events) must also be reported in English to Takeda Pharmacovigilance (or designee):

- Fatal and Life Threatening SAEs within 24 hours of the sponsor-investigator's observation or awareness of the event
- All other serious (non-fatal/non-life-threatening) events within 4 calendar days of the sponsor-investigator's observation or awareness of the event

See below for contact information for the reporting of SAEs to Takeda Pharmacovigilance.

The sponsor-investigator must fax or email the SAE Form per the timelines above. A sample of an SAE Form will be provided.

The SAE report must include at minimum:

- Event term(s)
- Serious criteria
- Intensity of the event(s): Sponsor-investigator's or sub-investigator's determination. Intensity for each SAE, including any lab abnormalities, will be determined by using the NCI CTCAE version specified in the protocol, as a guideline, whenever possible. The criteria are available online at <http://ctep.cancer.gov/reporting/ctc.html>.
- Causality of the event(s): Sponsor-investigator's or sub-investigator's determination of the relationship of the event(s) to study drug administration.

Follow-up information on the SAE may be requested by Takeda.

Intensity for each SAE, including any lab abnormalities, will be determined by using the NCI CTCAE version used at your institution, as a guideline, whenever possible. The criteria are available online at <http://ctep.cancer.gov/reporting/ctc.html>.

In the event that this is a multisite study, the sponsor-investigator is responsible to ensure that the SAE reports are sent to Takeda Pharmacovigilance (or designee) from all sites participating in the study. Sub-investigators must report all SAEs to the sponsor-investigator so that the sponsor-investigator can meet his/her foregoing reporting obligations to the required regulatory agencies and to Takeda Pharmacovigilance, unless otherwise agreed between the sponsor-investigator and sub-investigator(s).

Relationship to all study drugs for each SAE will be determined by the investigator or sub-investigator by responding yes or no to the question: Is there a reasonable possibility that the AE is associated with the study drug(s)?

Sponsor-investigator must also provide Takeda Pharmacovigilance with a copy of all communications with applicable regulatory authorities related to the study product(s), as soon as possible but no later than 4 calendar days of such communication.

SAE and Pregnancy Reporting Contact Information

[REDACTED]
[REDACTED]

Suggested Reporting Form:

- SAE Report Form (provided by Takeda)
- US FDA MedWatch 3500A:
[REDACTED]
- Any other form deemed appropriate by the sponsor-investigator

23.2 Product Complaints

A product complaint is a verbal, written, or electronic expression that implies dissatisfaction regarding the identity, strength, purity, quality, or stability of a drug product. Individuals who identify a potential product complaint situation should immediately contact Takeda

and report the event. Whenever possible, the associated product should be maintained in accordance with the label instructions pending further guidance from a Takeda Quality representative.

A medication error is a preventable event that involves an identifiable patient and that leads to inappropriate medication use, which may result in patient harm. While overdoses and underdoses constitute medication errors, doses missed inadvertently by a patient do not. Investigators must record all medication errors (including overdose) on the appropriate CRF form. Individuals who identify a potential medication error situation should immediately contact Takeda (see below) and report the event.

For Product Complaints or Medication Errors (Including Overdose)

- [REDACTED]
- [REDACTED]
- [REDACTED]
- [REDACTED]

Product complaints in and of themselves are not AEs. If a product complaint results in an SAE, an SAE form should be completed and sent to Takeda Pharmacovigilance.

23.3 Procedures for Reporting Drug Exposure During Pregnancy and Birth Events

If a woman becomes pregnant or suspects that she is pregnant while participating in this study or within 90 days after the last dose, she must inform the investigator immediately and permanently discontinue study drug. The sponsor-investigator must immediately fax a completed Pregnancy Form to the Takeda Department of Pharmacovigilance or designee. The pregnancy must be followed for the final pregnancy outcome.

If a female partner of a male patient becomes pregnant during the male patient's participation in this study, the sponsor-investigator must also immediately fax a completed Pregnancy Form to the Takeda Department of Pharmacovigilance or designee. Every effort should be made to follow the pregnancy for the final pregnancy outcome.

Suggested Pregnancy Reporting Form: Pregnancy Report Form (provided by Takeda)

24.0 STATISTICAL METHODS and ANALYSES

24.1 Analysis Population

The primary analysis population will be:

- **Safety Population:** All patients who provide written informed consent, and receive at least one dose of ixazomib

24.2 Hypothesis Testing

No formal hypothesis testing will be done.

24.3 Demographics and Baseline Disease Characteristics

The safety population will be used for the analysis of demographic and baseline disease characteristics data. Descriptive statistics will be used to summarize demographic and baseline patient characteristics. Continuous-scaled variables (e.g., age) will be summarized

with the number of observations (N), mean, standard deviation, median, quartile, and minimum and maximum. Categorical variables (e.g., sex) will be summarized using patient counts and percentages. Baseline medical histories and pre-existing conditions will be summarized based on mapping to system organ classes and preferred terms in the Medical Dictionary for Regulatory Activities (MedDRA). Prior medications will be summarized by titration group, based on mapping to drug classes and generic terms in the World Health Organization (WHO) Drug Dictionary.

24.4 Dosing and Duration of Exposure

The safety population will be used for the analysis of study drug dosing and duration of exposure. The total duration of exposure will be defined as the time interval between the first dose and the last dose of ixazomib (inclusive), based on the patient study drug dosing information. Total duration of exposure to study drug (in weeks) will be summarized by descriptive statistics (i.e., N, mean, standard deviation, median, quartile, and minimum and maximum).

The number and percentage of patients requiring dose reductions, modifications, and discontinuations will be summarized by group.

24.5 Safety Analyses

The safety population will be used for the analysis of safety data. Summaries of AEs, deaths, and patient disposition will be presented, comparing patients in the two treatment groups. Study periods will be comprised of the following:

- Entire 24-week study period
- First 12 weeks of treatment
- Subsequent 12 weeks of treatment

Safety measurements will include the following:

- Treatment-emergent AEs
- Treatment-emergent SAEs
- Treatment-emergent treatment-related AEs
- Treatment-emergent treatment-related SAEs
- Treatment-emergent AEs leading to ixazomib dose modifications
- Treatment-emergent AEs leading to early discontinuation of ixazomib
- Treatment-emergent changes in clinical laboratory measures
- Treatment-emergent changes in patient vital signs
- Treatment-emergent changes in UCLA SCTC GIT 2.0 questionnaire

AEs will be mapped to system organ classes and preferred terms in MedDRA. Treatment emergent events are defined as those that start or worsen after the start of study treatment through 28 days after the last dose of study treatment. AEs will be summarized by treatment group, system organ class, and preferred term, and by event severity and the event's relationship to study treatment. At each level of summation, patients will be counted only once, under the greatest severity and strongest study-drug relationship.

Clinical laboratory data will be summarized at each measurement time point and for each patient's final post-baseline measurement in the following ways:

- (1) with descriptive statistics (mean, standard deviation, median, and range) for each

measurement time point;

(2) with descriptive statistics for the change from baseline in the measurements at each post-baseline time point; and

(3) with tables summarizing the frequencies of patients below, within, and above the normal ranges at each time point as compared with baseline. All clinical laboratory values collected during the study will be listed, with values outside the normal ranges flagged for clinical evaluation. Grade 3 and 4 laboratory results will be listed and summarized.

Vital signs will be summarized by group and listed by patient.

Data from the UCLA SCTC GIT 2.0 questionnaire at each assessment time will be summarized descriptively without imputation for missing values.

Concomitant medications will be summarized by treatment group based on mapping to drugclasses and generic terms in the WHO Drug Dictionary.

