6.0 STUDY OBJECTIVES

6.1 Primary objective:

To determine the safety and tolerability of ixazomib 4 mg taken orally on days 1, 8, and 15 of a 28-day treatment cycle repeated for 6 cycles when administered to adult patients with scleroderma-related ILD as assessed by:

1. Physical examinations, vital signs, 12-lead ECG, echocardiogram, clinical laboratory tests, and pregnancy tests.
2. UCLA SCTC GIT 2.0 questionnaire [148, 149].
3. Averse event documentation.

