7.0 STUDY DESIGN

7.1 Overview

This is a phase 2 open-label, safety and tolerability pilot study of oral ixazomib in patients with scleroderma-ILD (SSc-ILD). Planned enrollment will be 12 patients who have been seen in the Mayo Clinic Arizona Scleroderma program among whom will be 6 participants already taking SSc-ILD background medication mycophenolate (MMF) at stable dose for at least 3 months, and 6 participants who either have not taken a SSc-ILD background medication within 3 months of study screening or by the time of study screening will complete medication washout of medications being taken for SSc-ILD other than MMF. The number of study candidates needing to washout medications other than MMF is anticipated to be very low based on the low prevalence of medicines other than MMF used clinically for the treatment of scleroderma-ILD. No study candidate already taking MMF will be asked to wash out MMF. Eligible participants include male and female adult patients at least 18 years of age, fulfilling the 2013 American College of Rheumatology (ACR)/European League Against Rheumatism (EULAR) criteria for systemic sclerosis/scleroderma [151] and having disease duration \leq 60 months based on first non-Raynaud's phenomenon manifestation. ILD is based on features observed from the participant's HRCT chest scan obtained within 3 months prior to either medication washout or screening visit, as applicable. Studyscreening

will include pulmonary function testing demonstrating FVC \geq 45% predicted and DLCO \geq 40% predicted, which will also be determined to be stable measurements as compared with previous pulmonary function testing obtained clinically within the prior 3-12 months. For the 6 study participants who are taking stable dose background MMF, the MMF will be continued at the same dose during the study. MMF will be prescribed as routine clinical care and will not be provided as part of the study. All 12 participants will be administered oral ixazomib. Ixazomib dose modification or interruption will be allowed for safety or tolerability reasons at any time during the study. Any patient who permanently and prematurely discontinues study treatment will also be discontinued from the study.

There are four study periods (all durations are in calendar days):

- **Washout Period:** \leq 90 days:
 - **Participants who are taking background SSc-ILD medication other than MMF at screening:**

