For participants taking no background SSc-ILD medication at study entry who need to begin a SSc-ILD medication and participants on background MMF at study entry who need either (1) to switch to another background SSc-ILD medication, or (2) to begin additional treatment with another background SSc-ILD medication, the new SSc-ILD medication will be prescribed as routine clinical care and will not be provided as part of the study.

Participants who prematurely and permanently discontinue ixazomib study treatment will return to the clinic as soon as possible after the last dose of ixazomib and not later than 10 days after that dose to complete early discontinuation assessments and procedures as planned for study day 168 (week 24) office visit (see 18.3.10).

Participants who prematurely and permanently discontinue ixazomib study treatment will

again return to the clinic 28-35 days after completing the study early discontinuation assessments and procedures visit to complete early discontinuation assessments and procedures as planned for study post-treatment follow-up day 196-203 (week 28-29) office visit (see 18.3.11).

Any patient who prematurely and permanently discontinues ixazomib study treatment will be discontinued from the study and will be encouraged to continue post-discontinuation monitoring if eligible to do so.

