17.2.5 Echocardiogram

If a resting transthoracic echocardiogram has not been done within 6 months prior to written informed consent at medication washout or screening, as applicable, it will be performed at screening.

17.2.6 University of California, Los Angeles, Scleroderma Clinical Trials Consortium Gastrointestinal Scale, 2.0, Questionnaire [148, 149]

The UCLA Scleroderma Clinical Trials Consortium Gastrointestinal Tract (UCLA SCTC GIT) 2.0 is a self-administered survey. The survey consists of 34 questions (Reflux 1 to 8, Distention/Bloating 9 to 12, Fecal Soilage 13, Diarrhea 14 to 15, Social functioning 16 to 21, Emotional well-being 22 to 30, Constipation 31 to 34). The items are scored on a scale from 0 to 3, where 0 indicates better health and 3 indicates worse health, except for questions 15 and 31, which are scored as 0 (better health) and 1 (worse health). Scores from all scales except the constipation scale are averaged to form a total GIT score from 0 (no gastrointestinal problems) to 3 (most severe) that captures overall burden of severity of SSc-associated GIT involvement.

The UCLA SCTC GIT 2.0 questionnaire will be used to obtain the participant's assessment of

the frequency of GI symptoms in the preceding 7 days and how those symptoms affected his/her life. The questionnaire will be administered during screening (see 8.2.1 Study Population Exclusion Criteria), at study Day 1, and at each subsequent study visit every 28 days (weeks 4-24). For the extension study, the questionnaire will be administered at study day 84 (week 36) and study day 168 (week 48) office visits.

17.3 Study Measures for the Secondary Objective to Assess the Clinical Efficacy of Ixazomib

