24.7 Post-Discontinuation Assessments for Safety

Participants who prematurely and permanently discontinue ixazomib study medication and continue with post-discontinuation monitoring visits will be used for the analysis of post-discontinuation safety data. Summaries of AEs, deaths, and patient disposition will be presented.

Safety outcome measures used will include, but will not be limited to:

- Treatment-emergent (not ixazomib) AEs
- Treatment-emergent (not ixazomib) SAEs
- Treatment-emergent (not ixazomib) treatment-related AEs
- Treatment-emergent (not ixazomib) treatment-related SAEs
- Treatment-emergent (not ixazomib) changes in clinical laboratory measures
- Treatment emergent (not ixazomib) changes in patient vital signs
- Treatment emergent (not ixazomib) changes in UCLA SCTC GIT 2.0 questionnaire

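### GIT 2.0, part of the primary safety objective, is summarised only by visit on observed data, so group means can shift when participants stop ixazomib; add each participant's worst and last change

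*Combined protocol and SAP*

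**What the plan says.** Section 6.1 lists GIT 2.0 second among the three means of assessing safety and tolerability. Section 24.1 defines the safety population as all consenting patients who receive at least one dose, and 24.5 uses that population. Changes in GIT 2.0 are a named safety measure in 16.1 and 24.5, but the only sentence on how to analyse them is "Data from the UCLA SCTC GIT 2.0 questionnaire at each assessment time will be summarized descriptively without imputation for missing values". Section 25.5.1 has the same sentence for the extension.

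Other measures in 24.5 are treated more fully. Laboratory data also get change from baseline at each time point and a summary of each patient's final post-baseline value. Adverse events are counted once per patient, at greatest severity.

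On stopping, section 7.1 says: "Any patient who permanently and prematurely discontinues study treatment will also be discontinued from the study". Section 15.0 requires a return visit "not later than 10 days after that dose to complete early discontinuation assessments and procedures as planned for study day 168 (week 24) office visit", and the day 168 list in 18.3.10 includes GIT 2.0. Section 15.1 then encourages, but does not require, visits every 28 days that also collect it. Those later scores belong to a separate analysis in 24.7, under the item "Treatment emergent (not ixazomib) changes in UCLA SCTC GIT 2.0 questionnaire". Section 25.5.3 does the same for the extension, which under 25.1 admits only participants still on ixazomib.

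**The concern.** Stopping ixazomib is plausibly linked to this outcome. Section 5.0 expects a higher risk of some GI events in scleroderma. Section 9.2.1 names diarrhea, nausea and vomiting as associated reactions, and 9.2.3.4 lets recurrent grade 2 or 3 non-hematologic events end in discontinuation. If participants with the worst GI symptoms are the ones who stop, a by-visit summary of observed scores comes to describe those who could stay on the drug. The primary objective asks about everyone dosed.

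The plan also sets the first 12 weeks against the second, and the MMF group against the no-MMF group, with about six participants in each. One departure can move such a comparison. Section 5.0 notes that MMF has overlapping GI effects, so departures may differ between the groups.

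**Working it through.** **Inputs from the plan.** Section 7.1: "Planned enrollment will be 12 patients", six on background MMF and six not. Section 17.2.6: the total score runs from 0 to 3, higher is worse, with recall over the preceding 7 days. Section 24.2: "No formal hypothesis testing will be done". The documents give no GI discontinuation rate, expected score or effect size, so there is no planned figure to reproduce. All scores and rates below are assumptions.

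**Shift when participants leave.** Let d of n leave, with mean score L for leavers and S for stayers, and let nobody's score change.
- Mean with all present: [(n − d)S + dL]/n. Mean afterwards: S.
- Shift = −(d/n)(L − S).

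**Example, n = 6, d = 1, S = 0.5, L = 1.5.**
- Before: (5 × 0.5 + 1.5)/6 = 4.0/6 = 0.67. After: 0.50. Shift: −(1/6)(1.0) = −0.167.

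**Range.**
- Gap of 1.0: −0.167 (1 of 6), −0.333 (2 of 6), −0.083 (1 of 12), −0.167 (2 of 12).
- One leaver of 6, gap 0.25 to 2.0: −0.042 to −0.333.

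**Direction is conditional.**
- Leaver equal to stayers (all at 0.5): 0.50 before and after.
- Leaver lower (five at 0.8, one at 0.3): (4.0 + 0.3)/6 = 0.717, then 0.800. The mean rises.

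**Change from Day 1 does not cure this by itself.** Put all six at 0.5 on Day 1; one rises to 1.5 and stops. Mean change is 1.0/6 = +0.167 while all are seen and 0.000 at visits after the stop. The mean of each participant's last change stays at +0.167.

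**How often could it arise?** The chance of at least one GI discontinuation is 1 − (1 − p)^n. For assumed p of 5%, 10%, 20% and 30% it is 26%, 47%, 74% and 88% in a group of 6, and 46%, 72%, 93% and 99% in all 12.

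**The unassigned score matters.** Suppose the leaver in the example stops after week 8 and scores 1.5 at the early-discontinuation visit.
- Tabulated at week 24: the means are 0.50 at weeks 12 to 20 and 0.67 at week 24.
- Tabulated at the nearest scheduled visit: one more mean of 0.67, then 0.50.
- Not tabulated by visit: 0.50 from week 12 on.

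The text allows all three.

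**The case against.** The strongest reply is that leavers are measured and reported. They owe a GIT 2.0 score within 10 days of the last dose, inside the plan's treatment-emergent window of 28 days. Because that visit follows the day 168 list, the score could be tabulated at week 24 and keep the intolerant participant in the final summary. Scores may also exist from on-treatment visits before the stop. Section 24.5 reports adverse events leading to dose modification and to discontinuation, and disposition; 24.4 counts reductions and discontinuations by group; 24.7 covers post-discontinuation scores. Nothing is tested, so no decision threshold hangs on a GIT mean.

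Much of this stands. A reader might infer that GIT 2.0 is analysed only in those who tolerate the drug, or that the GI signal is lost. The documents do not support either: the analysis set is everyone dosed, and the information is placed elsewhere.

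The reply does not close the gap. Counts of discontinuations show that someone left, not how bad that person's GI symptoms were. Post-discontinuation visits are voluntary, are counted from the early-discontinuation visit, and so do not line up with study visits. A participant's own choice to stop is not among the eligibility reasons listed in 15.1.1. The early-discontinuation score may also reflect recovery, given 7-day recall and up to 10 days off drug. After an interruption of more than 28 days for an adverse event, the 10-day limit cannot be met at all, and those provisions of 15.0 must be reconciled.

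**Conclusion.** The point holds as a gap in the analysis of a primary safety measure that is cheap to close. GIT 2.0 has no per-participant worst or last summary, and one collected score has no stated place. A group mean can therefore change because its membership changed. The size is illustrative: 0.67 to 0.50 for one leaver of 6 with a gap of 1.0 point, and −0.042 to −0.333 over gaps of 0.25 to 2.0.

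A reader might go further and say the plan biases GI tolerability in favour of ixazomib. That needs leavers to score worse than stayers. This is plausible from sections 5.0 and 9.2, but the documents give no rate or score that establishes it.

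**What to change.** In 24.5 and 25.5.1:
- For every dosed participant with a post-dose score, report the worst and the last GIT 2.0 change from Day 1, for the total and each domain, using all on-treatment visits plus the early-discontinuation visit. State how many dosed participants have no post-dose score.
- State where the early-discontinuation score is tabulated.
- Show n at each visit by group, with the last change of those who have left.

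The early-discontinuation score matters most in the extension. Section 17.2.6 schedules GIT 2.0 only at weeks 36 and 48 there, so someone who stops before week 36 may have no other extension score before post-discontinuation monitoring.

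No imputation and no new data collection are needed. The cost is SAP wording and one extra table. A worst-value summary is somewhat inflated by visit-to-visit noise and depends on the number of visits, which is why the last change should stand beside it. The reported GI burden may look slightly less favourable.
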